17.1.1. ALL TEAEs

Incidence of TEAEs will be presented by SOC and PT and broken down further by maximum severity and relationship to study medication.

17.1.1.1. Severity

Severity is classed as mild/ moderate/ severe (increasing severity). TEAEs starting after the first dose of study medication with a missing severity will be classified as severe. If patient reports a TEAE more than once within that SOC/ PT, the AE with the worst-case severity will be used in the corresponding severity summaries.

17.1.1.2. Relationship to Study Medication

Relationship, as indicated by the Investigator, is classed as “unknown”, “unrelated”, “unlikely to be related”, “possibly related” and “probably related” (increasing probability of relationship). A “related” TEAE is defined as a TEAE with a relationship to study medication as “possibly related” or “probably related” to study medication. TEAEs with a missing relationship to study medication will be regarded as “probably related” to study medication. If a patient reports the same AE more than once within that SOC/ PT, the AE with the worst case relationship to study medication will be used in the corresponding relationship summaries.

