- Mild: An event that is easily tolerated by the patient, causing minimal discomfort and not interfering with everyday activities.
- Moderate: An event that causes sufficient discomfort and interferes with normal everyday activities.
- Severe: An event that prevents normal everyday activities. An AE that is assessed as severe should not be confused with a SAE. Severe is a category utilized for rating the intensity of an event; and both AEs and SAEs can be assessed as severe.

An event is defined as ‘serious’ when it meets at least one of the predefined outcomes as described in the definition of an SAE, NOT when it is rated as severe.

Assessment of Chronicity

- Single occasion: Single event with limited duration.
- Intermittent: Several episodes of an event, each of limited duration
- Persistent: Event which remained indefinitely.

Assessment of Causality

- The Investigator is obligated to assess the relationship between blinded study medication and each occurrence of each AE/SAE. The AE must be characterized as unrelated, unlikely to be related, possibly related, probably related, or unknown (unable to judge).
 - “Probably related” conveys that there are facts, evidence, and/or arguments to suggest a causal relationship, rather than a relationship cannot be ruled out.
 - “Possibly related” suggests that the association of the AE with the blinded study medication is unknown; however, the AE is not reasonably supported by other conditions.
 - “Unlikely to be related” suggests that only a remote connection exists between the blinded study medication and the AE. Other conditions, including chronic illness, progression or expression of the disease state or reaction to concomitant therapy, appear to explain the reported AE.
 - “Unrelated” is used if there is not a reasonable possibility that the blinded study medication caused the AE.
 - All efforts should be made to classify the AE according to the above categories. The category “unknown” (unable to judge) may be used only if the causality is not assessable (eg, because of insufficient evidence, conflicting evidence, conflicting data, or poor documentation).
- The Investigator will use clinical judgment to determine the relationship.

- Alternative causes, such as underlying disease(s), concomitant therapy, and other risk factors, as well as the temporal relationship of the event to blinded study medication administration will be considered and investigated.

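### TEAEs with causality recorded as unknown are counted as not related, while a blank causality is counted as probably related

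*SAP*

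**What the plan says.** SAP 17.1.1.2 names five causality classes in the order unknown, unrelated, unlikely to be related, possibly related, probably related, and describes that order as "increasing probability of relationship". Three rules follow in the same paragraph:

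- Definition of related: "A “related” TEAE is defined as a TEAE with a relationship to study medication as “possibly related” or “probably related” to study medication".
- Blank field: "TEAEs with a missing relationship to study medication will be regarded as “probably related” to study medication".
- Same event reported more than once by a patient within a SOC/PT: "the AE with the worst case relationship to study medication will be used in the corresponding relationship summaries".

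Protocol Appendix 7 (Section 11.7, Assessment of Causality) says when the first class applies: "The category “unknown” (unable to judge) may be used only if the causality is not assessable". It names unknown after the four graded classes and gives it no rank among them. Protocol 9.4.2 asks for a summary of related AEs without defining related. SAP 3.3, which lists changes to the analysis from the protocol, does not mention the ranking.

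**The concern.** An event recorded as unknown and an event with an empty causality field tell the analyst the same thing about causality, which is nothing. The SAP sends the first to the not-related side and the second to the highest related class. Completing an empty field with unknown therefore moves an event from related to not related, although no judgement about the drug has been made.

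The stated order has a further fault. Under the protocol, unrelated is a positive judgement that the drug is not a reasonable explanation. Unknown is the absence of a judgement and cannot sensibly be less probable than that.

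At stake is how the related-TEAE tables by SOC and PT (SAP 17.1) and their repeat on the Extended Safety Set (SAP 17.7) are read. A reader who sees that missing causality is imputed as probably related will take these tables to be conservative. For unknown events they are not.

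**Working it through.** No sample size, power or alpha figure is involved, and the plan states no figure to reproduce. The check applies the rules of SAP 17.1.1.2 literally.

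**Step 1: each recorded value.**

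| Recorded causality | Place in SAP order | Counted as related |
|---|---|---|
| unknown | 1 | no |
| unrelated | 2 | no |
| unlikely to be related | 3 | no |
| possibly related | 4 | yes |
| probably related | 5 | yes |
| blank | 5 (as probably related) | yes |

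The exclusion of unknown comes from the definition of related. It stands even if the order is read as loose wording.

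**Step 2: repeated reports.** Five classes give 5 × 4 / 2 = 10 pairs. Unknown is in four of them and loses all four, so a patient with one unknown and one unrelated report of the same PT is shown as unrelated. With unknown placed between unlikely and possibly related, two pairs change: unknown with unrelated, and unknown with unlikely, are both shown as unknown. The other eight are unchanged. Under the SAP's present definition, unknown, unrelated and unlikely are all not related, so the ranking cannot change a related count. It changes only which row of the by-relationship breakdown (SAP 17.1.1) the patient appears in.

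**Step 3: size of the effect on related counts.** For a given SOC/PT and arm, let R be the number of patients with at least one possibly related, probably related or blank report. Let U be the number with at least one unknown report and none of those three. The SAP reports R. Counting unknown as related gives R + U, so the difference is exactly U. The documents give no value for U. Taking the planned 500 and 300 patients as approximate denominators, each such patient adds 1/500 = 0.2 percentage points to related incidence on ensifentrine, or 1/300 = 0.33 on placebo. If U is zero, nothing changes.

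**Step 4: the SAP's other rules for uncertainty.** Each of these resolves doubt towards the worst case or towards inclusion:

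- Undeterminable treatment emergence is taken as treatment-emergent (17.1).
- Missing severity is taken as severe (17.1.1.1).
- Missing causality is taken as probably related (17.1.1.2).
- Doubt about whether a patient was treated is resolved as treated, for the safety set (5.8).
- An equal split of treatments received is assigned to ensifentrine (6.7).

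Unknown causality goes the other way, and no reason is given.

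**The case against.** The best defence is that a blank is absent data and needs imputation, whereas unknown is a completed answer from the investigator. Leaving it out of related respects what was recorded, and counting it as related recodes it. The protocol's possibly related class also has content that unknown lacks: other conditions do not reasonably account for the event. Nothing in the documents requires unknown to count as related.

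Part of this stands. The grouping is an analysis choice and breaches no stated rule. But leaving unknown out of related is not neutral, because it puts an unassessable event on the same side as a judgement of no causation. The distinction between recorded and absent data does not explain why the recorded non-judgement gets the less cautious treatment.

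A reader might also infer three stronger things that the documents do not support:

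- **That the ranking lowers the related-TEAE counts.** It does not. The definition alone does that.
- **That unknown events disappear from reporting.** They remain in the all-TEAE tables and the listings. They also appear in the relationship breakdown unless a graded report of the same PT displaces them.
- **That serious or fatal events would be concealed.** This is speculation. Serious TEAEs and deaths are summarised regardless of causality (SAP 17.1.3 and 17.1.4), and Protocol Appendix 7 stresses that causality should be assessed for every SAE before its first transmission.

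**Conclusion.** The point holds as a minor one. The definition of related in SAP 17.1.1.2 is non-conservative for unknown events and inconsistent with the SAP's treatment of missing causality, missing severity and unclear treatment emergence. The position of unknown below unrelated is wrong against the protocol's definition, with the narrow consequence shown for repeated reports.

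The understatement in any related-TEAE row equals the number of patients whose only claim to related status is an unknown report. That number is expected to be small because the protocol asks for all efforts to use the graded classes first. This is an expectation from the wording, since no frequency is given. The Extended Safety Set tables carry the same rule and are not a separate problem. Safety outputs are descriptive with no planned between-group testing unless otherwise specified (SAP 17), so efficacy conclusions and type I error are untouched.

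**What to change.** Amend SAP 17.1.1.2 before unblinding:

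- Order causality for the worst-case rule as unrelated, unlikely to be related, unknown, possibly related, probably related, with missing still treated as probably related.
- Keep unknown as its own row in the relationship breakdown.
- Define a related TEAE as one recorded as possibly related, probably related or unknown, or with causality missing.

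The order and the definition should change together. If only the definition changed, a patient with an unknown and an unrelated report of the same PT would still be shown as unrelated in the breakdown while having an event that counts as related.

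The cost is a sentence or two in the SAP and a small programming change. Related-event counts may rise slightly, and some of the added events will have no real link to the drug. The separate row for unknown lets a reader see how many were added.

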17.1.2. TEAEs LEADING TO DISCONTINUATION OF STUDY MEDICATION

TEAEs leading to discontinuation of study medication are AEs recorded as “Study Treatment Permanently Discontinued” on the “Adverse Events” page of the eCRF.

For TEAEs leading to discontinuation of study medication, summaries of incidence rates (frequencies and percentages) by SOC and PT will be prepared.

17.1.3. SERIOUS ADVERSE EVENTS

Serious adverse events (SAEs) are those events recorded as "Serious" on the "Adverse Events" page of the eCRF. A summary of serious TEAEs by SOC and PT and by treatment group and different period (i.e. Treatment period, Follow-up and Overall) will be prepared.

17.1.4. ADVERSE EVENTS LEADING TO DEATH

TEAEs leading to Death are those events which are recorded as "Fatal" on the "Adverse Events" page of the eCRF. A summary of TEAEs leading to death by SOC and PT will be prepared.

17.2. LABORATORY EVALUATIONS

Results from the central laboratory (or local laboratory where this is required) will be included in the reporting of this study for chemistry, hematology and viral serology. A list of laboratory assessments to be included in the outputs is included in the Appendix 3 of the study protocol. Presentations of all laboratory tests will use standard international (SI) units. However, certain laboratory tests will also be presenting using US units, including liver tests. The handling of re-test and unscheduled measurements is detailed in section 6.4 of the SAP.

The following summaries will be provided for chemistry and hematology data:

- Actual and change from baseline by visit (for quantitative measurements)
- Incidence of abnormal values according to normal range criteria
- Shift from baseline according to normal range criteria (for quantitative measurements and categorical measurements)
- Shift from baseline according to markedly abnormal criteria (for quantitative measurements and categorical measurements)
- Listing of patients meeting markedly abnormal criteria

Viral serology, COVID-19 sample, chemistry and hematology will be listed.

L

FINAL v1.0
 25JUL2022

17.2.1. LABORATORY REFERENCE RANGES AND CLINICALLY SIGNIFICANT ABNORMAL CRITERIA

Quantitative laboratory measurements will be compared with the relevant laboratory reference ranges in SI units and categorized as:

- Low: Below the lower limit of the laboratory reference range.
- Normal: Within the laboratory reference range (upper and lower limit included).
- High: Above the upper limit of the laboratory reference range.

In addition to the high and low quantitative laboratory assignments (as identified by means of the laboratory reference ranges), clinically significant abnormal quantitative chemistry laboratory assessments will also be identified in accordance with the predefined markedly abnormal criteria as presented in Table 4.

If ULN or LLN have “ $\leq X$ ” or “ $\geq X$ ” then “X” will be used for analysis and “ $\leq X$ ” or “ $\geq X$ ” will only be used in listings.

Table 4: Clinically Significant abnormal criteria for laboratory parameters

[figure not shown]
Parameter	Clinically Significant Abnormally High Criteria
Alanine Aminotransferase (ALT)	> 3 times Upper Limit of Normal Range
Alkaline Phosphatase	> 3 times Upper Limit of Normal Range
Aspartate Aminotransferase (AST)	> 3 times Upper Limit of Normal Range
Creatinine	>221 $\mu\text{mol/L}$
Gamma Glutamyltransferase (GGT)	> 3 times Upper Limit of Normal Range
Total Bilirubin	> 3 times Upper Limit of Normal Range

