11.9 Appendix 9: Liver Safety

Phase III-IV liver chemistry stopping and follow-up criteria have been designed to assure patient safety and evaluate liver event etiology (in alignment with the FDA premarketing clinical liver safety guidance). Phase III-IV liver chemistry stopping criteria 1-5 are defined below. Investigators may at their discretion refer patients meeting liver safety criteria below to a specialist who may determine the appropriate or medically necessary additional or confirmatory laboratory tests or procedures as required by the protocol or otherwise deemed necessary (e.g. liver imaging).

1. ALT \geq 3xULN and bilirubin \geq 2xULN (35% direct bilirubin) (or ALT \geq 3xULN and INR $>$ 1.5, if INR measured).

Note: if serum bilirubin fractionation is not immediately available, withdraw study drug for that patient if ALT \geq 3xULN and bilirubin \geq 2xULN. Serum bilirubin fractionation should be performed if testing is available. If testing is unavailable, record presence of detectable urinary bilirubin on dipstick, indicating direct bilirubin elevations and suggesting liver injury.

2. ALT \geq 8xULN.
3. ALT \geq 5xULN but $<$ 8 xULN persists for \geq 2 weeks.
4. ALT \geq 3xULN if associated with symptoms (new or worsening) believed to be related to hepatitis (such as fatigue, nausea, vomiting, right upper quadrant pain or tenderness, or jaundice) or hypersensitivity (such as fever, rash or eosinophilia).
5. ALT \geq 5xULN but $<$ 8 xULN and cannot be monitored weekly for \geq 2 weeks.

When any of the liver stopping criteria 1-5 is met do the following:

- **Immediately** discontinue blinded study medication/investigational product for that patient.
- Report the event to IQVIA within 24 hours of learning its occurrence.
- Complete the liver event CRF and SAE data collection tool if the event also meets the criteria for an SAE. All events of ALT \geq 3xULN and bilirubin \geq 2xULN (35% direct bilirubin) (or ALT \geq 3xULN and INR $>$ 1.5, if INR measured); INR measurement is not required and the threshold value stated will not apply to patients receiving anticoagulants), termed 'Hy's Law' must be reported as an SAE (excluding studies of hepatic impairment or cirrhosis).

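### SAP Table 4 has no flag for total bilirubin from 2 to 3xULN and the SAP text describes no combined ALT/bilirubin output, so a protocol Hy's Law case can show in the markedly abnormal outputs as an ALT rise alone

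*SAP*

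**What the plan says.** SAP 17.2.1 grades chemistry results in two layers.

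- **Reference range.** Every quantitative test is classed Low, Normal or High: "High: Above the upper limit of the laboratory reference range".
- **Table 4.** This layer comes "In addition to the high and low quantitative laboratory assignments". ALT, AST, alkaline phosphatase, GGT and total bilirubin all carry the same entry, "> 3 times Upper Limit of Normal Range". Creatinine has its own limit. Each row concerns one test.

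SAP 17.2 plans outputs from both layers. From the reference range come "Incidence of abnormal values according to normal range criteria" and a shift table. From Table 4 come a second shift table and a "Listing of patients meeting markedly abnormal criteria". In addition, "Viral serology, COVID-19 sample, chemistry and hematology will be listed". For the Extended Safety Set, SAP 17.7 names markedly abnormal values for selected chemistry parameters as the only laboratory output.

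Protocol 11.9 (Appendix 9) defines stopping criterion 1 by two tests together. ALT is at or above 3xULN, and the bilirubin limb is at or above "2xULN (35% direct bilirubin". The alternative is ALT at or above 3xULN with INR above 1.5, if INR is measured. The appendix names this event Hy's Law and says that all such events "must be reported as an SAE (excluding studies of hepatic impairment or cirrhosis".

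**The concern.** The protocol singles out one liver event by name and makes its reporting as an SAE mandatory. The SAP's markedly abnormal screen is the natural place for a reader to look for it in the laboratory data, but the screen is not built on that definition. Its bilirubin limit is higher (above 3xULN, against at or above 2xULN). Its ALT limit is strict where the protocol's is inclusive. It also looks at each test separately, although the event is defined by both together.

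At stake is whether the planned laboratory outputs show, by arm, how many patients met the protocol's own definition. Without such an output, a reader of the markedly abnormal tables could take a combined elevation for an isolated ALT rise.

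**Working it through.** The plan states no figure to reproduce. The check applies each document's rule to the same pairs of values.

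**Inputs**

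- Protocol 11.9, criterion 1, bilirubin limb: ALT ≥ 3xULN and bilirubin ≥ 2xULN. The direct-fraction condition is assumed met.
- SAP Table 4: ALT flagged if > 3xULN; total bilirubin flagged if > 3xULN.
- SAP reference-range layer: High if > ULN.

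**Grid**

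ALT at 3.0, 3.1, 4 and 8xULN, crossed with bilirubin at 1.9, 2.0, 2.5, 3.0 and 3.1xULN, gives 4 × 5 = 20 pairs. The four pairs with bilirubin 1.9 fail the protocol rule, so 16 qualify.

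| ALT (xULN) | Bilirubin (xULN) | Pairs | Table 4 ALT flag | Table 4 bilirubin flag | Both High by reference range |
|---|---|---|---|---|---|
| 3.0 | 2.0, 2.5, 3.0 | 3 | no | no | yes |
| 3.0 | 3.1 | 1 | no | yes | yes |
| 3.1, 4, 8 | 2.0, 2.5, 3.0 | 9 | yes | no | yes |
| 3.1, 4, 8 | 3.1 | 3 | yes | yes | yes |

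The rows sum to 3 + 1 + 9 + 3 = 16. These are points chosen to test the boundaries, not expected frequencies.

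**Reading the result**

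1. For ALT above 3.0xULN and bilirubin from 2 to 3xULN, the patient is in the markedly abnormal listing, but of the two tests only ALT is marked.
2. For ALT exactly 3.0xULN and bilirubin from 2 to 3xULN, neither test is marked. This comes from the ≥ versus > boundary. Such a patient could still be flagged on another Table 4 row, for example AST or GGT.
3. Both tests are flagged only when each is above 3xULN. Even then, the SAP text describes no output that says the two elevations occurred together.
4. Every qualifying pair is High on both tests in the reference-range layer. That layer gives bilirubin of 1.1xULN and 2.9xULN the same label and works one test at a time, so its tables do not identify the combined event.
5. The INR alternative appears nowhere in Table 4. A case qualifying by that route would be marked by its ALT value only, unless bilirubin was also above 3xULN.

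**The case against.** The strongest case on the other side is that nothing is lost and nothing is contradicted. Section 11.9 is a rule for individual patients, while Table 4 is a descriptive screen. Table 4 also omits the protocol's 5x and 8xULN limits for ALT, so it was evidently not meant to mirror the appendix. The central laboratory measures total, direct and indirect bilirubin (Protocol 11.3, Table 13) and all chemistry is listed, so any pair of values can be read off. Section 11.9 also requires a liver event form and a report within 24 hours. Serious TEAEs are tabulated by arm (SAP 17.1.3) and repeated for the Extended Safety Set (SAP 17.7).

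Most of this stands, and it rules out three stronger readings that a reader might infer.

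- *A qualifying case can be absent from the abnormal-laboratory tables altogether.* It cannot: both values exceed ULN and are counted in the normal-range tables.
- *Detection rests entirely on site SAE reporting.* It does not: the chemistry listing allows direct review, and one of the two shift tables does not use Table 4.
- *No output anywhere pairs the two tests.* The documents cannot show this. SAP 8 leaves the format and content of outputs to a shells document, and SAP 1 refers to a separate pooled SAP. Neither is available here, so the statement is limited to the SAP text.

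A further fair objection is that a bare bilirubin limit of 2xULN would catch benign indirect elevation. Exclusion 12 makes an exception for Gilbert's syndrome, and exclusion 18 accepts isolated raised bilirubin with a direct fraction below 35%.

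The objection does not remove the gap itself. Reading line listings is not a by-arm summary. The serious TEAE tables depend on a site recognising, reporting and coding the event. The SAP text does not mention the liver event form.

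**Conclusion.** The point holds as a reporting gap. Table 4 leaves total bilirubin from 2xULN up to and including 3xULN without a markedly abnormal flag, differs from Protocol 11.9 at the ALT boundary, and has no companion output in the SAP text for the combined criterion. A case meeting criterion 1 in that bilirubin range therefore shows in the markedly abnormal outputs through ALT alone or, at ALT exactly 3.0xULN, through neither test.

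The number of patients affected cannot be worked out, because the documents give no expected rate of liver events. It is likely to be small among about 800 randomized patients. The conclusion assumes that the unseen shells add no combined display. It does not mean that cases would go unreported, or that the two documents conflict on patient management. The change is worth making because it is cheap and concerns the liver event that the protocol itself defines.

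**What to change.** Change the reporting only, leaving every stopping rule as it is:

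1. In Table 4, add a total bilirubin category at or above 2xULN and set ALT to at or above 3xULN.
2. Add a by-arm count and a patient listing, for the Safety and Extended Safety sets, of patients meeting protocol criterion 1: ALT at or above 3xULN with bilirubin at or above 2xULN, or with INR above 1.5 where measured.
3. Show the direct bilirubin fraction in that listing. The text of 11.9 as available gives 35% without a comparison sign, so displaying the fraction is safer than deriving a cut from it.
4. State how the values are paired in time. Section 11.9 gives no window; the same blood draw is the simplest rule.
5. AST may be shown as an additional category, labelled as outside criterion 1, which uses ALT only.

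The cost is one table edit and one derived flag. ALT, total bilirubin and direct bilirubin are already collected. A few more patients will be flagged, including some with benign indirect bilirubin elevation, and the direct fraction would identify them.
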